## 6.4 CONCOMITANT THERAPY

Not-applicable: Patients must have discontinued and be willing to remain off all other ophthalmic preparations including artificial tears during the study.

### 6.4.1 RESCUE MEDICINE

In the event that rescue medication is required for clinically relevant worsening of keratitis, patients will be provided a concomitant regimen the investigator/treating clinician can initiate:

- Flarex® 0.1% dosed four times a day for up to 10 days as recommended by the prescribing physician.

and

- Instillation of Hylo-Forte® in each eye 5 minutes prior to applying the study ointment. This can be maintained for the duration of the study as recommended by the prescribing physician.

Patients responding to treatment may remain in the study. Patients not-responding to treatment and who are still demonstrating clinically significant keratitis may be temporally discontinued from treatment or discontinued from the study at the investigator/treating clinician's discretion.

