Patients should refrain from using any ophthalmic preparations other than study treatment in order to obtain an accurate assessment of their signs and symptoms. Patients should be instructed to communicate any changes to their ophthalmic preparations other than study treatment at their next study visit.

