8.4 PRIOR AND CONCURRENT MEDICATIONS

All relevant prior and concomitant medications will be presented in a listing for the mITT population. Patients must have discontinued and be willing to remain off all other ophthalmic preparations including artificial tears during the study. In the event that rescue medication is required for clinically relevant worsening of keratitis, patients will be provided a concomitant regimen the investigator/treating clinician.

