9.2 PRIMARY EFFICACY SYMPTOM FOR MGD

The primary symptom for MGD is based on change from baseline in total OSDI at the 3-month follow-up between AZR-MD-001 group versus vehicle group. The primary efficacy symptom will be evaluated in

	TEMPLATE		
	DOCUMENT #:		TMP-191
	REVISION:		2.0
STATISTICAL ANALYSIS PLAN TEMPLATE	CC #:	836	PAGE 17 OF 25

the mITT and mITT2 populations and will be analyzed at month 3 using an analysis of covariance (ANCOVA) model with baseline OSDI, baseline MGS score stratum (<6 or ≥6) and duration of disease stratum (< 5 years or ≥ 5 years) as covariates and treatment group as factors in the model. The difference between treatment groups will be evaluated using t-tests of the least square means from this model. The two-sided confidence interval (95%) will be provided for the difference between treatments.

The following pseudocode will be used:

```
PROC GENMOD data=xxx;
BY visit;
CLASS treatment (ref = 'AZR-MD-001 VEHICLE') duration baseMGS;
MODEL chg = treatment base duration baseMGS;
LSMEANS treatment;
run;
```

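### Patients rescued for keratitis stay in the trial, yet the SAP uses their post-rescue OSDI and staining values as observed and plans no comparison of rescue by arm

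*Protocol*

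**What the plan says.** Protocol 6.4.1 describes two rescue products for clinically relevant worsening of keratitis. The steroid is "dosed four times a day for up to 10 days as recommended by the prescribing physician". The lubricant is instilled "in each eye 5 minutes prior to applying the study ointment", and for the lubricant alone the text adds "This can be maintained for the duration of the study as recommended by the prescribing physician". It then states: "Patients responding to treatment may remain in the study".

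The surrounding protocol text points the other way. Section 6.4 says "Patients must have discontinued and be willing to remain off all other ophthalmic preparations including artificial tears during the study". Section 5.3 gives the reason: "Patients should refrain from using any ophthalmic preparations other than study treatment in order to obtain an accurate assessment of their signs and symptoms". Section 5.1 requires corticosteroids used for dry eye or MGD, and tear substitutes, to have been stopped before screening.

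SAP 8.4 is the only SAP section that mentions rescue. It repeats the prohibition and the rescue provision, and the output it plans is this: "All relevant prior and concomitant medications will be presented in a listing for the mITT population". SAP 9.2 defines the symptom endpoint without reference to rescue: "The primary symptom for MGD is based on change from baseline in total OSDI at the 3-month follow-up". SAP 9.3.22 analyses corneal and conjunctival staining at every visit, also without reference to rescue.

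**The concern.** By the protocol's own reasoning in section 5.3, other ophthalmic preparations interfere with the assessment of signs and symptoms. A rescued responder is then assessed while using one, or after using one, and the plan has no rule for those values.

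Two things are at stake. First, interpretation. Rescue is triggered by worsening keratitis, so its use need not be balanced between arms. If the active ointment irritates the cornea more, the patients who tolerate it worst receive products that may lower OSDI and staining, and the arm looks better on both. If rescue falls mainly on vehicle, the shift goes the other way.

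Second, tolerability. The study objective leads with safety and tolerability. Needing rescue for keratitis is a direct marker of corneal intolerance, but it is not among the safety measures in Protocol 8.2.1 or SAP 3.2.3. Staining is classed as an efficacy measure, and its post-rescue grades may understate the problem.

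**Working it through.** **1. Exposure that the protocol permits.** The steroid is capped at 10 days. OSDI asks about the last week (Protocol 14.2). A steroid course therefore overlaps the Month 3 OSDI recall window only if it starts within about 10 + 7 = 17 days of that visit. The lubricant is tied to an ointment applied twice per week (Protocol 4.2.2), so as written it is about two instillations a week, possibly to study end.

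**2. A rescued responder followed through the SAP.**
- mITT entry (6.2) depends on MGS values. Rescue plays no part, so the patient is included.
- LOCF and multiple imputation (7.3) act on missing values. Post-rescue values are not missing, so they stand. If the patient later leaves, LOCF can carry a post-rescue value forward to Month 3.
- The OSDI model (9.2) contains treatment, baseline OSDI, duration stratum and MGS stratum. It has no rescue term or rule.
- The staining analysis (9.3.22) uses every visit as recorded.
- There is no per-protocol set. mITT2 (6.3) is defined by baseline MGS only.
- The medication listing (8.4) covers the mITT population, so a patient rescued early who left without a qualifying MGS value would not appear in it.

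**3. The plan's own figures.** Protocol 9.1 and SAP 4 give 12 per group for MGS (10.4 units, SDs 3.35 and 9.48) and 11 per group for OSDI (15.9 units, SDs 13.01 and 6.79), at 90% power and two-sided 0.05. An unequal-variance t-test reproduces both. For MGS, power is 91.4% at 12 and 88.4% at 11. For OSDI, it is 91.9% at 11 and 88.8% at 10. This point does not dispute the sample size.

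**4. Illustrative size for OSDI.** The documents give no rescue rate and no rescue effect, so both are assumed. Take 15 per arm (about 30 randomised 1:1), k = 1 to 3 more rescued patients in one arm, and d = 5 to 15 OSDI points per rescued patient.

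Shift in arm mean = k × d / 15
- Smallest: 1 × 5 / 15 = 0.33
- Largest: 3 × 15 / 15 = 3.0

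Against the planned 15.9: 0.33 / 15.9 = 2% and 3.0 / 15.9 = 19%.

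Against AZ201801 (Protocol 2.2, OSDI change of −6.9 on 0.5% and 0.0 on vehicle, difference 6.9): 0.33 / 6.9 = 5% and 3.0 / 6.9 = 43%.

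**5. Effect on the OSDI test.** With 15 per arm, the planning SDs and no true drug effect, the SE of the difference is √((13.01² + 6.79²) / 15) = 3.79. A shift of 1.0 raises the rejection rate of a standalone 0.05 test from 5.0% to 5.7%, and a shift of 3.0 raises it to 11.9%. Both figures are before the MGS gatekeeping step. In the other direction, a 2.0-point shift favouring vehicle turns a true 6.9 into 4.9, and power falls from 42% to 24%. Equal rescue with equal effect gives no shift.

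**The case against.** The case against has real force on several points.

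- **Steroid duration.** A reader might infer that both products can run to study end. They cannot: the open-ended sentence belongs to the lubricant only.
- **Lubricant exposure.** About two bedtime instillations a week is not daily tear therapy, so a large lasting effect on OSDI is far from certain.
- **Confounding.** A reader might call the symptom result confounded. That is too strong. Rescue occurs after randomisation, and analysing observed values gives a valid randomised comparison of two strategies, each including rescue as needed. The documents never claim that the values reflect study drug alone.
- **MGS.** A reader might extend the point to the primary sign. The documents offer no mechanism by which these products would change gland secretion, and MGS gates the OSDI test.
- **Magnitude.** The 43% needs the top of both assumed ranges and the smaller reference difference. A 15-point rescue effect exceeds the 12-point difference reported for the 1.0% dose. If the ± values in Protocol 2.2 are independent standard errors, the SE of the 6.9 is √(4.0² + 3.4²) = 5.25, so 0.33 to 3.0 points is about 0.06 to 0.57 SE.
- **Other safety outputs.** Concomitant medication is a coded adverse-event action (Protocol 8.3.3.3), and the adverse-event listing shows action taken (SAP 11.1). Biomicroscopy shifts and the comfort questionnaire are also planned.
- **The contradiction.** Section 6.4.1 sits under 6.4 and can be read as its exception.

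These points limit the size and wording of the concern. They do not supply what is missing. The treatment-policy choice is stated nowhere. The adverse-event route depends on keratitis being recorded as an event, and Protocol 8.3.1 leaves room not to do so where worsening is captured by efficacy assessments or is no more than expected for the disease. Nothing planned gives a count of rescued patients by arm.

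**Conclusion.** The point stands for OSDI and corneal staining and for the reporting of rescue as a tolerability outcome. Followed exactly, the plan cannot separate a study-drug effect on these measures from a rescue effect, and it does not compare rescue between arms. It does not follow that the randomised comparison is invalid, that the steroid may run to study end, or that the MGS result is affected.

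Size and direction are unknown. The 0.3 to 3.0 points rest wholly on assumed numbers of rescued patients and assumed effects. The shift would be zero with balanced rescue of equal effect and would reverse if rescue were commoner on vehicle. The change should be made because a handful of patients can matter with about 15 per arm and the remedy is small.

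**What to change.** Keep the primary analysis and state in the SAP that it is treatment-policy with respect to rescue. Then:

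1. **SAP 9.2 (OSDI):** add one prespecified sensitivity analysis that sets values after first rescue to missing, with no LOCF, and imputes them with the multiple imputation model in SAP 7.3. Run it whenever any patient is rescued, whether or not the 5% missing-data trigger is met. Two details of that model need settling. Its Month 3 TBUT predictor would itself be post-rescue in these patients, and its listed predictors do not include treatment arm. Do not assign zero change: the imputation should use each patient's own pre-rescue course.
2. **SAP 9.3.22 (staining):** in the matching analysis, use the worst grade recorded up to and including the time of rescue in place of later grades.
3. **SAP 10:** for the safety population, report by arm the number and percent rescued and the time to first rescue.
4. **Protocol 5.3, 6.4 and 6.4.1:** reconcile these on whether other ophthalmic preparations are permitted during the study. This review takes no view on what the clinical rule should be.

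The cost is some SAP text, one extra analysis for each of the two endpoints and one table. Medications are recorded at each visit under the schedule of activities. The case report form is not among the documents, so the availability of rescue start dates is an assumption to confirm. The downside is that the sensitivity estimate may be less favourable if rescue falls mainly in the active arm.

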## 7 STUDY INTERVENTION DISCONTINUATION AND PARTICIPANT DISCONTINUATION/WITHDRAWAL

### 7.1 DISCONTINUATION OF STUDY INTERVENTION

Patients can voluntarily withdraw from the study at any time. The investigator and Azura Ophthalmics can withdraw a patient from the study at any time for any reason. Additionally, patients can be discontinued from the study by an investigator if any of the following criteria are met:

- patient develops (or had an exacerbation of) any medical condition that, in the opinion of the investigator, would have put the patient at an unacceptable medical risk or compromised the patient's ability to participate in the study
- patient is unwilling or unable to continue to comply with study procedures

- patient becomes pregnant

The study can be stopped at the study site(s) at any time by the site investigator(s). Azura Ophthalmics can also stop the study (and/or the study site[s]) with appropriate notification.

If a patient discontinues participation in the study early, every attempt must be made to complete the exit procedures. Notification of early patient discontinuation from the study and the reason for discontinuation should be made to Azura Ophthalmics and should be clearly documented on the appropriate eCRF.

## 7.2 PARTICIPANT DISCONTINUATION/WITHDRAWAL FROM THE STUDY

The investigator and Azura Ophthalmics have the right to withdraw a patient from the study at any time for any reason. When possible, the decision to withdraw a patient from the study should be discussed with Azura Ophthalmics.

Patients who are withdrawn early from the study should have early exit visit procedures completed at the time of withdrawal, or at their next scheduled visit, whenever possible.

## 7.3 LOST TO FOLLOW-UP

A patient will be considered lost to follow-up if he or she fails to return for 2 consecutive scheduled visits and is unable to be contacted by the study site staff.

The following actions must be taken if a participant fails to return to the clinic for a required study visit:

- The site will attempt to contact the participant and reschedule the missed visit within the specified visit window (see Table 1.3) and counsel the patient on the importance of maintaining the assigned visit schedule and ascertain if the participant wishes to and/or should continue in the study.
- Before a patient is deemed lost to follow-up, the investigator or designee will make every effort to regain contact with the participant (where possible, 3 telephone calls and, if necessary, a certified letter to the patient's last known mailing address or local equivalent methods). These contact attempts should be documented in the patient's medical record or study file.
- Should the patient continue to be unreachable, he or she will be considered to have withdrawn from the study with a primary reason of lost to follow-up.

## 8 STUDY ASSESSMENTS AND PROCEDURES

### 8.1 EFFICACY ASSESSMENTS

#### 8.1.1 PRIMARY EFFICACY MEASURES

*Primary Sign for MGD:*

- Change from Baseline to month 3 in meibum gland secretion score (MGS) (0 to 45 scale)

*Primary Symptom for MGD:*

- Change from Baseline to month 3 in Total OSDI

#### 8.1.2 SECONDARY EFFICACY MEASURES

*Secondary efficacy measures include:*

- Change from Baseline to day14, month 1 and month 1.5 in MGS (0 to 45 scale)
- MGS score (0 to 45 scale) at each visit
- Proportion of patients with a MGS score > 12 at each visit
- Change from Baseline to day14, month 1, month 1.5 and month 3 in the number of Meibomian Glands Yielding Liquid Secretion (MGYLS) (0 to 15 scale)
- MGYLS (0 to 15 scale) at each visit
- Change from Baseline to day 14, month 1, month 1.5, and month 3 in TBUT
- TBUT at each visit
- Proportion of patients with a TBUT score > 5 at each visit
- Change from Baseline to day 14, month 1, month 1.5 and month 3 in Standard Patient Evaluation of Eye Dryness (SPEED)
- SPEED at each visit
- Proportion of patients with a SPEED < 6 at each visit
- Change from Baseline to day 14, month 1, month 1.5 and month 3 in average visual analogue scale (VAS)
- Average VAS at each visit
- Change from Baseline to day 14, month 1, month 1.5 and month 3 in worst VAS
- Worst VAS at each visit
- Change from Baseline to day 14, month 1 and month 1.5 in Total OSDI
- Total OSDI, OSDI sub-scales, and individual items from the OSDI across visits
- Proportion of patients with a Total OSDI change from baseline > 4.5, the known minimally important clinical difference (MICD) for early to moderate disease, at month 3
- Proportion of patients with a Total OSDI < 13 at each visit
- Number of expressible glands yielding clear meibum at day14, month 1, month 1.5, and month 3
- Eyelid margin erythema/telangiectasias at day14, month 1, month 1.5, and month 3
- Corneal and conjunctival staining (0 to 5 scale) at each visit

### 8.1.3 DATA REVIEW COMMITTEE (DRC)

Not applicable.

## 8.2 SAFETY AND OTHER ASSESSMENTS

### 8.2.1 SAFETY MEASURES

*The following safety measures will be examined:*

- Adverse events
- Vital signs
- Study medication tolerability as measured by the Ocular Comfort Questionnaire
- Urine pregnancy test
- Best-corrected visual acuity (BCVA; Logarithmic visual acuity chart)
- Biomicroscopy
- Ophthalmoscopy
- Intraocular pressure (IOP)

## 8.3 ADVERSE EVENTS AND SERIOUS ADVERSE EVENTS

Adverse events occurring during the study will be recorded on an adverse event case report form (CRF). If adverse events occur, the first concern will be the safety of the study participants.

All adverse events that are drug-related and unexpected (not listed as treatment-related in the current Investigator's Brochure) must be reported to the governing Institutional Review Board/Independent Ethics Committee (IRB/IEC) as required by the IRB/IEC, local regulations, and the governing health authorities. Any adverse event that is marked 'ongoing' at the exit visit must be followed-up as appropriate.

### 8.3.1 DEFINITION OF ADVERSE EVENTS (AE)

An AE is defined as any untoward medical occurrence in a clinical study subject administered a medicinal product which does not necessarily have a causal relationship with this treatment. An AE can therefore be any unfavorable and unintended sign (including an abnormal laboratory finding), symptom, or disease temporally associated with the use of a medicinal (investigational) product, whether or not it is related to the medicinal (investigational) product. This includes an exacerbation of pre-existing conditions or events, intercurrent illnesses, drug interaction or the significant worsening of the indication under investigation that is not recorded elsewhere in the CRF under specific efficacy assessments. Anticipated fluctuations of pre-existing conditions, including the disease under study that do not represent a clinically significant exacerbation or worsening need not be considered AEs.

It is the responsibility of the investigator to document all AEs that occur during the study. AEs will be elicited by asking the subject a nonleading question, for example, "Have you experienced any new or changed symptoms since we last asked/since your last visit?". AEs should be reported on the appropriate page of the CRF.

Some illustrate examples follow to help understand the difference between events meeting the definition of an AE and those that don't.

**Events meeting AE definition include:**

- Any abnormal laboratory test results (hematology, clinical chemistry, or urinalysis) or other safety assessments (e.g., ECGs, radiological scans, vital signs measurements), including those that worsen from baseline, and felt to be clinically significant in the medical and scientific judgement of the investigator.
- Exacerbation of a chronic or intermittent pre-existing condition including either an increase in frequency and/or intensity of the condition.
- New conditions detected or diagnosed after study treatment administration even though it may have been present prior to the start of the study.
- Signs, symptoms, or the clinical sequelae of a suspected interaction.
- Signs, symptoms, or the clinical sequelae of a suspected overdose of either study treatment or a concomitant medication (overdose per se will not be reported as an AE/SAE unless this is an intentional overdose taken with possible suicidal/self-harming intent. This should be reported regardless of sequelae).
- "Lack of efficacy" or "failure of expected pharmacological action" per se will not be reported as an AE or SAE. However, the signs and symptoms and/or clinical sequelae resulting from lack of efficacy will be reported if they fulfil the definition of an AE or SAE.

**Events NOT meeting definition of an AE include:**

- Any clinically significant abnormal laboratory findings or other abnormal safety assessments which are associated with the underlying disease, unless judged by the investigator to be more severe than expected for the subject's condition.
- The disease/disorder being studied or expected progression, signs, or symptoms of the disease/disorder being studied, unless more severe than expected for the subject's condition.
- Medical or surgical procedure (e.g., endoscopy, appendectomy): the condition that leads to the procedure is an AE.
- Situations where an untoward medical occurrence did not occur (social and/or convenience admission to a hospital).
- Anticipated day-to-day fluctuations of pre-existing disease(s) or condition(s) present or detected at the start of the study that do not worsen.

### 8.3.2 DEFINITION OF SERIOUS ADVERSE EVENTS (SAE)

If an event is not an AE per the definition above, then it cannot be an SAE even if serious conditions are met (e.g., hospitalization for signs/symptoms of the disease under study, death due to progression of disease, etc).

An SAE is any untoward medical occurrence or effect that, at any dose,

- Results in death.
- Is life-threatening (an AE is life-threatening if the subject was at immediate risk of death from the event as it occurred, i.e., it does not include a reaction that might have caused death if it had occurred in a more serious form).
- Requires or prolongs inpatient hospitalization. (Complications occurring during hospitalization are AEs and are SAEs if they cause prolongation of the current hospitalization. Hospitalization for elective treatment of a pre-existing non-worsening condition is not, however, considered an AE. The details of such hospitalizations must be recorded on the medical history or physical examination page of the CRF).
- Results in persistent or significant disability/incapacity. (An AE is incapacitating or disabling if it results in a substantial and/or permanent disruption of the subject's ability to carry out normal life functions).
- Results in a congenital anomaly/birth defect.

In addition, medical and scientific judgement is required to decide if prompt notification is required in situations other than those defined for SAEs above. This may include any event that the investigator regards as serious that did not strictly meet the criteria above but may have jeopardized the subject or required intervention to prevent one of the outcomes listed above, or that would suggest any significant hazard, contraindication, side effect, or precaution that may be associated with the use of the investigational product.

#### 8.3.2.1 REPORTING OF SERIOUS ADVERSE EVENTS

Any SAE must be reported by the investigator if it occurs during the clinical study or within 30 days of receiving the study drug, whether or not the SAE is considered to be related to the investigational product. An SAE report consists of the SAE form, the AE form, medical history and the concomitant medication form. A copy of these forms must be faxed or e-mailed within 24 hours for the attention of the CRO. The appropriate pages in the eCRF must be completed as soon as possible. The CRO will handle the SAE as per the Safety Management Plan and ensure

appropriate review and onward reporting to the Sponsor, with oversight of reporting to the ethics committees and competent authority as per local regulatory requirements:

For medical emergencies contact: [name]

[contact]

E-Mail: [[contact]](mailto:[contact])

The investigator should not wait to receive additional information to document fully the event before notification of a SAE, though additional information may be requested. Where applicable, information from relevant laboratory results, hospital case records, and autopsy reports should be obtained.

Instances of death, congenital abnormality, or an event that is of such clinical concern as to influence the overall assessment of safety, if brought to the attention of the investigator at any time after cessation of study drug administration and linked by the investigator to this study, should be reported to the study monitor.

The sponsor and/or CRO will promptly notify all relevant investigators and the regulatory authorities of findings that could adversely affect the safety of subjects, impact on the conduct of the study or alter the independent ethics committee (IEC)/institutional review board (IRB) approval/favorable opinion of the study. In addition, CRO, on behalf of the sponsor, will expedite the reporting to all concerned investigators, to the IECs/IRBs, where required, and to the regulatory authorities of all adverse reactions that are both serious and unexpected.

Details of the procedures to be followed if a pregnancy occurs are provided in Section 8.3.7.

